The study is a randomized, comparative open label study to evaluate effect size and time course of treatment response for RLS-IAD over 6 weeks with a 46-week follow-up extension. Two medications and placebos will be used with equal random assignment to both groups

- Ferumoxytol intravenous (IV) 1020 mg – 2 vials of 510 mg (IV push, 2-3 mins) each given 2-7 days apart
- Ferrous sulfate 325 mg (oral) tabs morning and evening.
- Placebo: oral vitamin C 500 mg tabs, Saline infusion

Primary outcome is the CGI-2 score at 6 weeks after treatment starts. IV ferumoxytol 1020 mg treatment (2 separate doses 510 mg 2-7 days apart) will be offered to those not significantly responding (CGI-2 scores less than much or very much improved) at 6 weeks after oral-iron treatment and still meeting all requirements for entry to study. All responders will be followed for 12 months after treatment.

Study Objectives

Primary objectives

1. Determine relative effect sizes of standard IV and oral iron treatment of RLS with iron deficiency anemia for the PGI-2/CGI-2 (much and very much improved) and for IRLS scores
2. Determine time course of treatment response for IRLS, PGI-1 and PGI-2 scores

Secondary objectives

1. Estimate survival times for effective treatment (no return to other RLS medications) for 1 year after treatment
2. Evaluate possible predictors of treatment response
 - a. Iron status or iron response
 - b. IRLS severity
 - c. Subject characteristics (age, gender)
 - d. Medical factors affecting iron status

Tertiary/exploratory objectives

1. Evaluate significance of efficacy differences if any between oral and IV iron treatments at 6 weeks after treatment: Hierarchical testing first for the percentage with CGI-2 of much or very much improved and second for change from baseline in the IRLS score.
2. Evaluate efficacy benefits of each treatment for usual outcomes related to RLS morbidity: sleep, fatigue, quality of life, and mood.
3. Compare lymphocytes of RLS-IAD and non RLS-IAD for differences in iron related proteins.

Study Procedures

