Placebo: Normal Saline will be administered following exactly the same procedure as that for IV iron.

Agent and administration for oral iron and placebo

Oral iron: This study will use Ferrous sulfate 325 mg tablets. The medication is to be taken together twice a day. If significant stomach distress occurs the patient may elect to take the medication with food and must then notify the research coordinator. The pills will be provided in opaque bottles with exactly enough for 7 weeks and a pill count will be made at the 6-week follow up to determine compliance. The oral pills will be stopped at the 6-week evaluation time.

Placebo: Standard vitamin C 250mg, given in the same bottle as the oral iron.

Subject schedule: (See appendix for chart of visits)

There will be 2 – 3 visits at the [name] clinic and telephone evaluations conducted by the Hopkins doctors prior to the start of treatment. After the first IV treatment there will be a telephone evaluation at 1, 2 and 4 weeks later and a clinic visit for blood tests at 4 weeks after the first of the pairs of IV treatment and again at about 6 weeks after the first of the pair of IV iron treatments. At 6 weeks after treatment responders will continue in the study with telephone evaluations of their RLS symptoms and medications at about 3, 6, 9 and 12 months after the first IV treatment. At 6 weeks after treatment non-responders will be given the option of receiving the IV ferumoxytol following the same procedure as at the initial treatment with a 6-week period of observation except this will be open label. Both the patient and the coordinator will know that ferumoxytol was given at this repeat dosing. This option will be given only if the patient continues to meet all the inclusion/exclusion criteria for the study noted below, except they will not be excluded for their prior IV treatment in this study. Those receiving the repeat IV dosing at 6 weeks will follow all the same procedures used after the first IV dosing, e.g. telephone safety checks and RLS symptom evaluations at 24-48 hours, 1 week and 4 weeks after initial treatment and a repeat clinic visit at about 6 weeks after the first of the two repeated IV treatment. This 6-week clinic visit will repeat blood tests, adverse event reporting and clinical evaluation of the RLS. The responders to this repeated IV treatment will be followed for up to one year following the same procedures as responders. The non-responders will end the study at this point.

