Any other medical condition that, in the opinion of Investigator, may cause the subject to be unsuitable for the completion of the study or place the subject at potential risk from being in the study, e.g. a malignancy, uncontrolled hypertension, unstable ischemic heart disease, or uncontrolled diabetes mellitus

Study Endpoints for each subject

The following are endpoints for each patient in the study :

1. At evaluation in the clinic at about 6 weeks after the first IV iron treatment.
2. Termination of participation because of significant adverse effect from the IV infusion in the hour observed after the infusion.
3. Significant adverse event after starting the iron treatment and before the 6 week follow-up evaluation that was judged to require ending the study.
4. Subject decision not to continue in the study after the treatment and before the final evaluation.
5. [name] decision that it would be harmful to the patient to continue in the study.
6. Patient is non-compliant with study requirements and [name] judges this non-compliance is enough to significantly alter evaluation of the treatment. (Note that stopping the

18 July 2014

oral medication because of intolerance to the treatment is not considered non-compliance, but rather an outcome for the study. Patients discontinuing oral medication for adverse effects may qualify for repeat IV treatment.)

Duration of subject participation:

Participation will continue for 6 weeks after treatment for the primary study and for 12 months after treatment for the extension study for those responding to the initial treatments or the open label repeated IV treatment.

Early termination of study:

Subjects may terminate the study at any time or maybe terminated from the study for non-compliance or if continuation in the study is judged by [name] to be harmful to the patient. A telephone evaluation will be scheduled when possible at the time of early termination. The reason for the early termination will be noted.

Blood tests obtained:

Iron panel, hemoglobin and hematocrit will be obtained from morning fasting venous samples at screening prior to treatment and at 4 and 6 weeks after the first treatment. About 15 ml of blood will be obtained for these tests

An additional 24 ml of blood will be collected for lymphocytes the day of the first IV treatment before the treatment and again at 6 weeks after the treatment.

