The percentage responding will be evaluated for each drug condition to determine overall effect size at 6 weeks after treatment. This will be calculated for the IRLS scale and the PGI as change from baseline and for the CGI with response determined as much or very much improved (scores of 1 or 2). All scores greater than 2 on the CGI are considered to indicate no significant response. The onset of treatment will be described as the percentage showing much or very much improvement at each of the evaluations and by the change in IRLS score from baseline at each evaluation. The duration of treatment over the 12 month follow up will be described as the percentage of responders and the IRLS change from baseline at each time point for both oral and IV iron. The oral iron treatment will be stopped for all subjects at the 6-week time point.

The outcomes for the oral versus IV treatments at 6 weeks will be compared using a standard unpaired unequal variance t-test for the change in IRLS scores from baseline. The number of responders compared to no-responders will be compared using the Fisher Exact test.

Sample Size

Uncontrolled experience observing IDA patients with RLS indicated that about 80% responded to IV iron (about 1000mg dose) and 50% responded to standard oral iron treatment over 6 to 12 weeks. These percentage outcomes require a sample size of 70 (35 with each treatment) to provide a power of >80% with alpha = 0.05 to test for differences between these treatments. This was considered a reasonable sample to ascertain the effect size of the two treatments and to provide enough positive outcomes to evaluate time course for improvement with treatment and persistence of the treatment effect.

Breaking the blind

The randomization is in cohort blocks of 10, 5 with each treatment. The blind for the form of initial treatment will be broken for every cohort of 10 treated patients after all members of a cohort have completed the study. The blind may also be broken for specific subjects if the treatment information is needed for medical care of the patient.

Concomitant Medication

Permitted Medications

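### The 12-month duration summary by oral and IV iron rests on responders and re-treated responders only, with no stated denominator and no rule for classing re-treated patients

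*Protocol*

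**What the plan says.** Protocol, Statistical Analyses: duration over the 12-month follow-up "will be described as the percentage of responders and the IRLS change from baseline at each time point for both oral and IV iron". No denominator, analysis set or test is named for that period. The t-test and Fisher's exact test in the same section are for week 6.

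Who is followed after week 6:
- Study Design: "All responders will be followed for 12 months after treatment".
- Duration of subject participation: the extension is "for those responding to the initial treatments or the open label repeated IV treatment".
- Subject schedule: "The responders to this repeated IV treatment will be followed for up to one year following the same procedures as responders". Of those who do not respond to the repeat course it says "The non-responders will end the study at this point".

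No later evaluation is scheduled for a week-6 non-responder who does not take the repeat course.

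Who may be re-treated is put in two ways. Study Design makes the offer to "those not significantly responding (CGI-2 scores less than much or very much improved) at 6 weeks after oral-iron treatment". Subject schedule says "At 6 weeks after treatment non-responders will be given the option of receiving the IV ferumoxytol", without naming an arm, and the Summary is equally general. Subject schedule adds a condition: "This option will be given only if the patient continues to meet all the inclusion/exclusion criteria".

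Secondary objective 1 is the one-year survival of effective treatment, judged by whether patients go back to other RLS drugs. The SAP describes a six-week study, and its Statistical analysis section contains no 12-month efficacy analysis.

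**The concern.** Entry to the long-term follow-up depends on an outcome measured after randomisation, and the Sample Size section expects that outcome to differ by arm. Oral responders and IV responders are therefore selected groups, and differences between them at months 3 to 12 cannot be credited to the assigned treatment. The IRLS change after week 6 can be computed only in patients still contacted. Set beside the week-6 mean for all patients, it may look better simply because the non-responders have gone.

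Re-treatment adds a labelling problem. Classed by assignment, a re-treated oral patient puts a response that followed IV iron into the oral figures. Classed by treatment received, the same patient puts a non-randomised oral non-responder into the IV figures. The clock is also open. Subject schedule dates the follow-up calls from the first IV treatment, and a re-treated patient has two such dates. Month 3 (about 13 weeks) from the first is only about 13 − 6 = 7 weeks from the second.

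This follow-up is the trial's only long-term efficacy information. The Sample Size section gives persistence of effect as one reason for the chosen number, and the Risk Benefit section hopes to indicate a preferred treatment.

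**Working it through.** The plan gives no figure for the 12-month summary, so there is none to reproduce. The steps below use its planning rates to size the problem.

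**Inputs from the Protocol (Statistical Analyses, Sample Size):** 35 per arm; week-6 response p = 0.80 (IV) and 0.50 (oral).

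**Assumptions, not in the documents:** uptake of re-treatment u = 25% to 100%; response to the repeat course r = 50% to 80%; persistence of response to month 12, d, as stated in steps 4 and 5.

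**1. Initial responders.** IV: 35 × 0.80 = 28. Oral: 35 × 0.50 = 17.5, leaving 17.5 oral non-responders.

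**2. Re-treated oral non-responders who enter follow-up** = 17.5 × u × r.
- Low: 17.5 × 0.25 × 0.50 = 2.2. High: 17.5 × 1.00 × 0.80 = 14.
- Share of the followed oral cohort, by assignment: 2.2/(17.5 + 2.2) = 11% to 14/(17.5 + 14) = 44%.
- Share of the followed IV cohort, by treatment received: 2.2/(28 + 2.2) = 7% to 14/(28 + 14) = 33%.

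These shares do not depend on the number per arm, so the SAP's additional accrual does not change them.

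**3. If IV non-responders may also be re-treated** (Subject schedule wording): 35 × 0.20 = 7 are available. Then 7 × 0.25 × 0.50 = 0.9 to 7 × 1.00 × 0.80 = 5.6 more enter, which is 0.9/28.9 = 3% to 5.6/33.6 = 17% of the IV-assigned cohort.

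**4. Effect of the denominator.** Among responders the figure is d. Among all randomised, with week-6 non-responders counted as not sustained, it is p × d.
- d = 70% in both arms: responders-only 70% vs 70%. All randomised: 0.80 × 0.70 = 56% (IV) vs 0.50 × 0.70 = 35% (oral), a gap of 21 points.
- d = 60% IV and 70% oral: responders-only favours oral by 10 points. All randomised: 0.80 × 0.60 = 48% vs 0.50 × 0.70 = 35%, which favours IV by 13 points.

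**5. Sensitivity to the planning rates.** With a common d the all-randomised gap is d × (p_IV − p_oral). At d = 0.70 it falls from 21 points to 0 as the week-6 rates converge. Equal rates would remove this gap. They would not make the two responder groups comparable, because different kinds of patient may respond to each treatment.

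**The case against.** The strongest reply is that this is a description in a pilot. No 12-month test is planned, secondary objective 1 names no contrast between arms, and the Rationale makes treatment differences a tertiary goal. Duration of response is also naturally conditional on having responded. All of that stands, and the responder-only summary is worth keeping. A side-by-side description still needs a stated denominator and a statement of what it conditions on.

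A reader might infer that the plan pools oral non-responders into one of the arms. It does not say so. The text on re-treated patients concerns their follow-up procedures, and reporting them separately would be consistent with it. The gap is the missing rule. Separate reporting would settle the labelling but leave the selection of responders.

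The responder percentage could also be read as a percentage of all patients, with those who left counted as non-responders, which gives 56% vs 35% in the example. That reading is open, which is why the denominator must be stated. It cannot rescue the IRLS change, which needs a measurement.

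The 44% and 33% are ceilings. Re-treatment requires the entry criteria still to be met, including the haemoglobin limit, and the Rationale expects anaemia to recover with six weeks of oral iron. Full uptake is therefore unlikely.

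Finally, the Rationale calls the planning effect sizes provisional, and SAP Table 4 reports a mean clinician global score of 2.1 in both groups (p = .80). The responder imbalance behind the example may not have occurred. This limits the size of the problem but leaves the missing definitions in place.

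**Conclusion.** The point holds as a defect of definition and selection in a descriptive secondary analysis. By-arm IRLS change after week 6 is conditional on response and not protected by randomisation. The denominator for the responder percentage, the class of re-treated patients and their time origin are all unstated, and the SAP does not supply them.

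At the 80% and 50% planning rates, re-treated oral non-responders would be 11–44% of the oral cohort by assignment or 7–33% of the IV cohort by treatment received. With 70% persistence assumed in both arms, the choice of denominator moves the display from no difference to 21 points. These sizes rest on provisional response rates and on assumed uptake, repeat response and persistence.

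Two stronger readings are not supported. The documents plan no formal 12-month comparison of the arms, and they do not show that the oral arm will in fact look more durable than it was. The week-6 analysis is not affected. The change should be made because the by-arm duration figures cannot be interpreted without it.

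**What to change.** State the following in the Protocol's Statistical Analyses section and in the SAP:

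- **(a) All randomised.** At months 3, 6, 9 and 12, report sustained response by assigned arm with every randomised patient in the denominator. Count week-6 non-responders, and anyone given open-label IV iron, as not sustained. Name the measure: a collected response or IRLS score, together with objective 1's criterion of not going back to other RLS drugs. This needs care because the Protocol collects the clinician rating at every post-treatment contact, while the SAP says it was obtained only at week 6.
- **(b) Initial responders.** Report duration and IRLS change separately in this group, labelled as conditional on response and not a randomised comparison.
- **(c) Re-treated patients.** Report them as a separate, non-randomised group, with time counted from their first open-label dose.

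The Protocol's Study Design (offer after oral iron) must be reconciled with its Summary and Subject schedule (offer to non-responders generally), since this decides which arms feed group (c).

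The cost is wording and a re-tabulation, with no new visits. It is subject to missing data: the SAP reports 21 patients terminated or lost to follow-up, and global scores missing in 30. It tabulates no efficacy results for months 3 to 12. The durability percentages will look less favourable than responders-only ones.

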RLS patient ascertainment: A standard patient completed RLS diagnostic questionnaire is given to all of the patients at the [name] clinic as part of their routine clinical evaluation not limited to its use in this study. This questionnaire has a sensitivity and specificity of 87% and 94% respectively [11]. The patients identified by the questionnaire as probable RLS will be checked for meeting the inclusion criteria (see below). They will, If they meet criteria, be approached by the research coordinator to consent to this treatment protocol. If they consent then the

18 July 2014

coordinator will assign them a protocol number and will obtain any needed blood samples. The coordinator will review the clinical history with the patient to ensure they meet inclusion criteria. If they qualify as determined by inclusion/exclusion criteria (see below) the coordinator will schedule the patient for both a validated telephone diagnostic interview [12] by an RLS specialist at Johns Hopkins and two treatment times to occur 2 – 7 days apart starting after the interview. If the Hopkins interview confirms the RLS diagnosis the treatments will be given as scheduled. If the Hopkins interview does not confirm the diagnosis of RLS the patients participation in this study will end and routine care will be given.

Randomization. A table randomizing assignment of participants in order entered will be used to determine group placement. Once a patient has been confirmed with RLS by the telephone clinical interview they will be given an appointment for IV treatment. At the time of IV treatment the subject will be assigned to either IV or oral iron treatment based on the order in the randomized table. The randomization will be in 7 blocks of 10 with equal treatments in each block. The nursing staff will follow the randomization table based on the order of the subjects tested. Each subject will be assigned a study number at the time of the IV treatment. The subject data will be evaluated using this study number and not the protocol number assigned by the coordinator at the time the patient consented to the study.

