Patients continuing in the one year follow up will be followed for RLS symptoms over the entire year. The telephone evaluation at 12 months after treatment will end the study for these patients. Appendix A provides a flow sheet of the subject's schedule.

Subject population

Subjects with diagnosis of RLS and iron deficiency anemia

Inclusion criteria:

1. Aged \geq 18 years
2. Diagnosis of RLS based on questionnaire and confirmed by Hopkins Telephone Diagnostic Interview conducted by [name] or [name]
3. Iron deficiency anemia defined as ID either ferritin < 20 mcg/l, Tsat $<19\%$, anemia Hgb < 13 for both males and females.
4. Willingness to use contraceptive to avoid pregnancy: Women have to be surgically sterile, post menopausal or use one of the following contraceptives during the whole study period and after the

18 July 2014

study has ended for at least 5 times plasma biological half-life of the investigational medicinal product: intrauterine devices or hormonal contraceptives (contraceptive pills, implants, transdermal patches, hormonal vaginal devices, or injections with prolonged release).

5. Willingness to participate and signing the informed consent form

Exclusion criteria:

A subject will not be eligible for inclusion in this study if they fulfill any of the following criteria:

1. Iron overload or disturbances in utilization of iron (e.g. haemochromatosis and haemosiderosis)
2. Decompensated liver cirrhosis or active hepatitis (ALAT > 3 times upper limit of normal)
3. Serum ferritin > 500 ng/mL or transferrin saturation >40 %
4. Active acute or chronic infections (assessed by clinical judgment that may be indicated by White Blood Cells (WBC) and C-Reactive Protein (CRP) when these are available)
5. Rheumatoid arthritis with symptoms or signs of active inflammation
6. Pregnant and nursing women
7. History of multiple allergies
8. Known hypersensitivity to parenteral or oral iron or any excipients in the drug products
9. Previous IV iron treatment for RLS
10. Other iron treatment or blood transfusion within 4 weeks prior to the screening or treatment visit
11. Planned elective surgery during the study
12. Current (past 4 weeks) use of drugs that treat RLS, e.g. opioids, alpha-2-delta anti-depressants, dopaminergics (dopamine promoters, dopamine antagonists/blockers)

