July 18, 2014

Title: Pilot study: randomized, placebo-controlled comparator trial of IV vs oral iron treatment of RLS with Iron deficiency anemia. (IVOR-IDA)

Principal Investigator: [name].

INTRODUCTION

Summary: The restless legs syndrome (RLS), also known as Willis-Ekbom Disease, occurs in 40-50% of patients with iron deficiency (ID) or its end stage, iron deficiency anemia (IDA) (Achebe, AJH, 2023). Treatment correcting the ID is expected to also be effective for reducing or eliminating the RLS with IDA. Two accepted treatments for IDA, oral ferrous sulfate and ferumoxytol were compared for efficacy and speed of response for treatment of RLS occurring with IDA (RLS-IDA). The original plan for this study was the accrual of 70 RLS-IDA patients to be randomly assigned 35 each to oral or IV iron using double-blind, double-dummy procedures. The primary outcome was determined at 6 weeks of treatment. Following initial evaluation, due to complications of performing a clinical trial during the pandemic and the death of the principal investigator, it was determined that the patient and clinical global impression scores, primary outcomes for the trial, were missing in 30 patients. As a result, in order to maintain the prespecified statistical analysis, an additional 30 patients were accrued.

Background: Low iron status is associated with RLS. RLS has been documented to have significant decreased iron concentrations in the substantia nigra (Allen, Neurology, 2001) and other areas (Rizzo, Movement Disorders, 2013). These associations have been documented into studies using both magnetic resonance imaging (Allen, Rizzo, [name] Sleep Med 2006) and ultrasound (Schmidauer, Ann Neuro 2005). Peripheral iron status also relates to RLS severity (Sun, Sleep 1998) and both oral and IV iron treatments significantly reduce RLS symptoms compared with placebo (Allen, Sleep Med 2011 and Wang, Sleep Med 2009).

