A xcel-generated randomization table was used to randomly assign subjects to one of two treatment conditions. Blinding was done by a separate and independent "treatment nurse" who used the randomize table, made the assignments on the day of treat and then completed the appropriate treatment. The randomization was in 7 blocks of 10 with equal treatments in each block. The research coordinator did not know the treatment administered and was not present during treatment and did not have access to files indicating, which treatment was administered. During IV infusions, the patients wore sleep masks that fully covered their eyes to ensure they did not notice any color differences between the iron and placebo administration. All investigators and the Analysts were blind to the assignment until completion of the analysis.

Two IV treatments spaced 2-7 days apart were administered. These were either ferumoxytol or placebo. At the time of the first infusion, an opaque bottle containing either vitamin C or ferrous sulfate was given to the subject. The patient was instructed to take each of the pills twice a day for the next six weeks. Enough pills to last 7 seven weeks were given to allow for ongoing treatment for the follow-up appointment at six weeks after the first IV infusion.

For IV iron treatment, the commercially available ferumoxytol was used. Ferumoxytol is marketed as an iron replacement formulation indicated for the treatment of iron deficiency anemia and is FDA approved for this indication. Ferumoxytol (30 mg/mL) is available for IV injection in single use vials containing 510 mg of elemental iron in 17 mL. Ferumoxytol is stored at controlled room temperature (20-25° C). Pre-treatment medications were not administered. 510 mg of ferumoxytol was diluted in 100 ml normal saline and administered with an infusion pump over a 15-minute period. Vital signs were measured and recorded immediately prior to drug administration and were observed for 60 minutes following completion of the infusion with observation for signs or symptoms of adverse events. For the placebo (normal saline) administration was exactly the same procedure as the IV iron formulation.

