Change in hemoglobin and iron parameters for all subjects and by group are shown in Table 3. The mean change in hemoglobin from baseline to follow up was 1.2 (SD 1.3) for Group A and 6.0 (17.2) for Group B. The mean change in Ferritin from baseline to follow up was 200.3 and 23.3 for Group A and Group B, respectively. The mean change in TSAT from baseline to follow up was 16.5 and 12.2 for Group A and Group B, respectively. The mean change in MCV from baseline to follow up was 24.2 and -17.6 for Group A and Group B, respectively. There was a significant difference between follow up ferritin and TSAT values. Group A had a higher follow up ferritin values ($p=0. <0.0001$) and higher TSAT ($p=0.007$) values compared to Group B.

Table 4 shows the changes in patient severity scores from baseline to follow up, and the follow up patient and clinical global impression scores for all subjects and by group. No significant differences between the 2 groups in terms of change in (1) patient severity score from baseline to follow up, (2) follow up patient global impression score, or (3) clinical global impression score were observed.

Table 5 shows the change in FSS from baseline to follow up. There were no significant differences between the 2 groups in terms of change in FSS.

Table 6 shows the change in IRLS score from baseline to follow up for all subjects and by group. Group B had a greater reduction in IRLS score from baseline to follow up compared to Group A

NOT SURE IF/HOW YOU WANT TO PRESENT THE ADVERSE REACTION DATA

Commented [VS1]: These are results from my original analysis. I still need to double check the results. However, before doing so, I want to confirm that there are no new data to analyze.

Commented [VS2]: Will define "Group A" and "Group B" once I know which group is which

TABLES**Table 1. Baseline hemoglobin and iron parameters for all subjects and by group.**

	Total	Group A	Group B	P-value¹
Hemoglobin	N=93	N=47	N=46	0.14
Mean (SD)	11.1 (1.5)	11.3 (1.3)	10.8 (1.6)	
Median (IQR)	11.6 (10.2, 12.2)	11.7 (10.8, 12.3)	11.6 (9.7, 12.1)	
Min, Max	7.0, 13.1	7.2, 13.1	7.0, 13.0	
Ferritin	N=91	N=45	N=46	0.017
Mean (SD)	17.9 (16.7)	22.6 (19.6)	13.5 (12.1)	
Median (IQR)	11.0 (7, 24)	19 (7, 29)	10.0 (7-15)	
Min-Max	3, 102	4, 102	3.0, 59.0	
TSAT	N=92	N=46	N=46	0.025
Mean (SD)	10.4 (6.2)	11.4 (5.9)	9.5 (6.5)	
Median (IQR)	9.0 (6, 13)	10.0 (8, 15)	8.5 (6.0-11.0)	
Min-Max	2, 36	2, 36	2, 32	
MCV	N=93	N=47	N=46	0.233

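### The protocol breaks the blind block by block rather than at the end of the trial, and this conflicts with the SAP's statement that investigators and analysts stayed blind until the analysis was complete

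*Protocol*

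**What the plan says.** Protocol, Breaking the blind: the code for initial treatment "will be broken for every cohort of 10 treated patients after all members of a cohort have completed the study". A separate sentence allows individual codes to be opened for medical care.

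Protocol, Study Procedures (Randomization): "The randomization will be in 7 blocks of 10 with equal treatments in each block", and "The nursing staff will follow the randomization table based on the order of the subjects tested". The blocks therefore fill one after another.

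When a patient has completed is not defined in the unblinding rule. The Subject schedule section says of patients in the extension: "The telephone evaluation at 12 months after treatment will end the study for these patients". The section on duration of participation gives two horizons: "Participation will continue for 6 weeks after treatment for the primary study and for 12 months after treatment for the extension study", the latter for responders.

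SAP, Methods: "All investigators and the Analysts were blind to the assignment until completion of the analysis". In a margin comment in the SAP Results, the analyst will define the group labels "once I know which group is which".

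The SAP Summary explains that global impression scores were missing in 30 patients and continues: "As a result, in order to maintain the prespecified statistical analysis, an additional 30 patients were accrued".

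**The concern.** The protocol rule is rolling: each block is opened when its own members finish. The SAP describes a seal that held to the end. If the rule was followed and the codes reached investigators or analysts, the SAP sentence is wrong. If it was not followed, neither document says so.

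CGI is a clinician's judgement, and IRLS and PGI are patient-reported. The protocol collects all three at the telephone contacts up to month 12 as well as at week 6. Two routes to bias follow:

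- **Direct.** If completion means the 6-week visit, responders in an opened block have a known allocation while they are still being rated to month 12.
- **Indirect.** Staff who see arm-level results accumulate can carry expectations into later patients' ratings. The protocol sets no barrier between the opened codes and the raters or investigators.

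The protocol treats the between-arm comparison as exploratory. The SAP, however, makes CGI-I and IRLS change co-primary and reports p-values by group, so readers will rely on the blinding statement.

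**Working it through.** **1. Block arithmetic.** 7 × 10 = 70 patients and 7 × 5 = 35 per arm, which agrees with the protocol's sample size. The rule therefore gives up to seven openings. The plan states no figure for the overlap or for repeated looks.

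**2. Overlap with later ratings.** Inputs are 70 patients in treatment order, a primary rating 6 weeks after first treatment, and completion at C weeks. The accrual duration, A weeks, is not in the documents; I assume uniform accrual.

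- Block 1 is opened at A/7 + C.
- Patient *i* is first treated at *i*A/70 and has the 6-week rating at *i*A/70 + 6.
- The last patient's 6-week rating follows the opening if A + 6 > A/7 + C, that is, if A > 7(C − 6)/6.

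Thresholds:

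- C = 6: A > 0. Patients 11 to 70 are treated after patient 10, so all 60 are rated after the opening at any accrual rate.
- C = 52: A > 7 × 46/6 = 53.7 weeks.
- C = 58 (a repeat IV course at week 6, then 52 weeks; my reading): A > 7 × 52/6 = 60.7 weeks.

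Later patients, out of 60, with the 6-week rating after block 1 is opened (those not yet treated at that time in brackets):

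| Accrual A | C = 6 | C = 52 | C = 58 |
|---|---|---|---|
| 52 weeks | 60 (52) | 0 (0) | 0 (0) |
| 78 weeks | 60 (55) | 19 (14) | 14 (8) |
| 104 weeks | 60 (56) | 30 (25) | 25 (21) |

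**3. Overlap with follow-up ratings.** The last patient's month-12 call, if that patient is a responder, falls at A + 52. With C = 52 this is later than A/7 + 52 for any A > 0. With C = 58 it is later once A exceeds 7 weeks. Overlap with follow-up is thus close to certain on either reading; overlap with the primary rating is conditional.

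**4. Repeated looks, illustration only.** Suppose each opening led to an unadjusted test of the accumulated data at two-sided 0.05 (the protocol gives alpha 0.05 without sidedness). The simulated chance of at least one false positive over seven looks is:

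- z-test: 0.165 (400,000 runs)
- Welch t-test, planned for IRLS change: 0.169 (20,000 runs)
- Fisher exact test, planned for CGI response, common response rate 50%, 65% or 80%: 0.082, 0.078 and 0.062 (200,000 runs each), against 0.025 to 0.030 for a single final Fisher test

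Holding 0.05 over seven equally spaced looks with a constant threshold would need about 0.013 per look.

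**5. The two blinding statements.** The protocol rule is a plan in the future tense, and the SAP sentence is a report in the past tense. They can be reconciled only if the rule was not applied, or if the opened codes were kept from investigators and analysts. Neither document says either.

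**The case against.** The strongest reply is that the rule may never have been used. The SAP reports conduct, and the analyst's comment shows coded groups at the time of writing, which supports the SAP sentence. The Subject schedule also points to month 12 as the end of study for responders, and on that reading overlap with the 6-week rating needs slow accrual. Opening a finished block reveals no allocation in a later one. The treatment nurse knew assignments by design, so the SAP's claim covers only investigators and analysts. All of this stands. It limits what can be concluded, but it neither removes the rule nor explains its absence from the SAP.

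A reader might infer more, and the documents do not support it:

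- **That codes were opened early because the SAP Rationale remarks that IV iron did not do better.** The CGI and PGI results in Table 4 show no group difference, so the remark could be written without knowing which arm was which.
- **That follow-up ferritin (means 223.4 and 37.1 in Table 2) proves the point.** That gap could identify the arms with the list fully sealed. It is a separate matter.
- **That the 30 extra patients were added on sight of unblinded results.** The SAP attributes them to missing global impression scores and, in Methods, to terminations and losses.
- **That the trial's type I error was about 17%.** No interim test is planned and none is reported, so the IRLS p-value of 0.047 in Table 6 cannot be discounted on this ground.

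**Conclusion.** The point holds as a defect in a stated rule and an unreconciled conflict between the two documents. It is not evidence that blinding was broken. The overlap with follow-up ratings follows from sequential blocks. The overlap with primary ratings covers all 60 later patients on the 6-week reading. On the 12-month reading it begins once accrual passes about 54 weeks, assuming uniform accrual. The protocol's 2014 date and the SAP's account of hiatuses and later accrual make long accrual plausible, but no enrolment dates are given. The error rates of about 17% (t-test) and 6–8% (Fisher) describe looks that nobody planned, and serve only to show what the rule leaves open.

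**What to change.** Protocol, Breaking the blind: replace the block rule with *the allocation list stays sealed until the database for all randomised patients is locked, except for the individual medical-need unblinding that the protocol already allows*.

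SAP, Methods: state whether any block was opened and, if so, when and to whom, including whether this was before the 30 patients were added. If any was opened, correct the blinding sentence and label the between-arm p-values nominal. If none was, say that the protocol's rule was not applied. Because the SAP is written in the past tense, this disclosure is what matters most for reading the present results.

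The cost is a sentence or two in each document. The only loss is that arm-level information by block becomes available later; unblinding for medical need is unchanged.
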